#### 7.2.2 Visit 3 (Week 4)

Visit 3 will occur at 4 weeks ( $\pm$  3 days) from the first dosing date. During this visit, the following assessments/procedures will be performed:

- SIBDQ
- Mayo score (stool frequency, rectal bleeding, physician's global assessment)
- Record of AEs and concomitant medications
- Confirmation of fecal samples
- Review of returned study drugs and subject diary
- Vital signs (including temperature)
- Physical examination (including weight)
- 12-lead ECG
- Blood sampling for clinical lab tests (serum chemistry, hematology, pregnancy, and CRP)
- Blood sampling for pharmacokinetics: pre-dose, 3 and 6 hours post-dose
- Administration of study drug
- Distribution of a fecal sample collection containers for V4 (Week 8) sample
- Distribution of study drugs and subject diary

#### 7.2.3 Visit 4 (Week 8)

Visit 4 will occur at 8 weeks ( $\pm$  3 days) from the first dosing date. During this visit, the following assessments/procedures will be performed:

- SIBDQ
- Mayo score (stool frequency, rectal bleeding, endoscopic findings [flexible proctosigmoidoscopy/colonoscopy], physician's global assessment)

- UCEIS
- Record of AEs and concomitant medications
- Confirmation of fecal samples
- Review of returned study drugs and subject diary
- Vital signs (including temperature)
- Physical examination (including weight)
- 12-lead ECG
- Blood sampling for clinical lab tests (serum chemistry, hematology, pregnancy, and CRP)
- Blood sampling for pharmacokinetics: pre-dose
- Endoscopy which can be performed within 3 days before this visit if it is not feasible at the same date of Visit 4
- Biopsy sampling for histologic assessment and tissue concentration during the endoscopy.
- Distribution of a fecal sample collection containers for V5 (Week 12) sample
- Distribution of study drugs and subject diary

#### 7.2.4 Visit 5 (Week 12)

Visit 5 will occur at 12 weeks ( $\pm$  3 days) from the first dosing date. During this visit, the following assessments/procedures will be performed:

- SIBDQ
- Mayo score (stool frequency, rectal bleeding, physician's global assessment)
- Record of AEs and concomitant medications
- Confirmation of fecal samples
- Review of returned study drugs and subject diary
- Vital signs (including temperature)
- Physical examination (including weight)
- 12-lead ECG
- Blood sampling for clinical lab tests (serum chemistry, hematology, pregnancy, and CRP)
- Distribution of a fecal sample collection container for Visit 6 (Week 16) sample
- Distribution of study drugs and subject diary

#### 7.2.5 Visit 6 (Week 16)

Visit 6 will occur at 16 weeks ( $\pm$  3 days) from the first dosing date. During this visit, the following assessments/procedures will be performed:

- SIBDQ
- Mayo score (stool frequency, rectal bleeding, physician's global assessment)
- Record of AEs and concomitant medications
- Review of any changes in smoking habits of subject during the study period
- Confirmation of fecal samples
- Review of returned study drugs and subject diary

- Vital signs (including temperature)
- Physical examination (including weight)
- 12-lead ECG
- Blood sampling for clinical lab tests (serum chemistry, hematology, pregnancy, and CRP)
- Scheduling of the SFU visit at 2 weeks (+ 7 days) from the last dosing

### **7.3 Safety Follow-Up (SFU) Visit**

SFU visit will occur at 2 weeks (+7 days) from the date of last dose. During this visit, the following assessments/procedures should be performed:

- Record of AEs and concomitant medications
- Vital signs (including temperature)
- Blood sampling for clinical lab tests (serum chemistry, hematology, and pregnancy)

### **7.4 Early Termination (ET) Visit**

If a patient will drop-out the study before the last treatment visit, the clinical site will try to schedule an ET visit. During this visit, the following assessments/procedures should be performed:

- SIBDQ
- Mayo score (stool frequency, rectal bleeding, endoscopic findings [flexible proctosigmoidoscopy/colonoscopy] - if applicable, physician's global assessment)
- Record of AEs and concomitant medications
- Review of any changes in smoking habits of subject during the study period
- Confirmation of fecal samples, if applicable
- Review of returned study drugs and subject diary
- Vital signs (including temperature)
- Physical examination (including weight)
- 12-lead ECG
- Blood sampling for clinical lab tests (serum chemistry, hematology, pregnancy, and CRP)
- Endoscopy (biopsy), only if this ET occurs before Visit 4 (Week 8), which can be performed within 3 days before or after this visit if it is not feasible at the same date of ET Visit (if applicable)
- UCEIS (if the endoscopy is performed)
- Scheduling of SFU visit at 2 weeks (+ 7 days) from the last dosing unless this ET visit occurs after 2 weeks from the last dosing.

## **8 STUDY PROCEDURES**

### **8.1 Informed Consent and Medical History**

#### **8.1.1 Informed Consent**

The investigator will obtain informed consent and complete an ICF for each patient screened for this study. All patients will be informed in writing of the nature of the protocol and investigational therapy, their possible hazards, and their right to withdraw at any time, and will sign an ICF indicating their consent to participate prior to the initiation of study procedures. The patient's medical record should contain written documentation indicating that informed consent was obtained. The ICF must be reviewed and approved by the investigator's designated IRB and by the Sponsor. The ICF should include all the elements as outlined in Section 4.8.10 of the ICH guideline for GCP (E6).

#### **8.1.2 Medical History**

At screening, a complete medical history including a full history of UC will be collected by patient interview. Concomitant medications, recent blood donations, illnesses, and participation in other investigational drug studies will also be recorded.

Prior therapies related to UC and a detailed history of UC, including date of diagnosis, disease severity, hospitalizations, and extraintestinal manifestations will be collected during screening.

### **8.2 Safety Assessments**

- Physical examination: Screening, Baseline, W4, W8, W12, and W16
- Vital signs: All visits (including SFU)
- 12-lead ECG: Screening, Baseline, W4, W8, W12, and W16
- Clinical laboratory testing of serum chemistry/hematology: All visits (including SFU)
- Recording of AEs: W4, W8, W12, W16, and SFU

#### **8.2.1 Physical Examination**

Complete physical examination including weight, general appearance, examination of skin, HEENT (head, ears, eyes, nose, throat), lungs (auscultation), heart (auscultation for presence of murmurs, gallops, rubs, peripheral edema), abdomen (palpation and auscultation), neurology (mental status, station, gait, reflexes, motor and sensory function, coordination), and lymph nodes will be performed.

Any clinically significant changes from the baseline examination should be recorded as AEs.

### 8.2.2 Vital Signs

Vital signs will be recorded throughout the study as per the Schedule of Assessments. Blood pressure (BP) will be measured in the patient's dominant arm and recorded to the nearest mmHg. The same arm will be used throughout the study. All BP in this study will be measured with the patient in the sitting position after resting for at least 5 minutes. The use of automated devices for measuring BP and pulse rate are acceptable, although, when done manually, pulse rate will be measured in the brachial/radial artery for at least 30 seconds. On visits when a blood sample is collected, the BP and pulse rate should be obtained prior to blood sample collection.

Temperature will be recorded as either oral, axillary or tympanic temperature, with the same method used throughout the study.

### 8.2.3 Electrocardiogram (ECG)

Twelve (12)-lead ECGs will be obtained on all patients as per Schedule of Assessments. All scheduled ECGs should be performed after the patient has rested quietly for at least 10 minutes in a supine position.

ECG measurement collected at the Screening visit will serve as the patient's baseline value if conducted within 10 days prior to baseline. To ensure patient safety, a qualified individual at the investigator site will make comparisons to the baseline measurement.

If the QTc measurement at a time post-dose is  $> 45$  msec increase from the baseline; or an absolute QTc value is  $\geq 500$  msec for any scheduled ECG, a single ECG will be repeated at least hourly until QTc values from successive ECGs fall below the threshold value that triggered the repeat measurement.

In some cases, it may be appropriate to repeat abnormal ECGs to rule out improper lead placement as a factor of the ECG abnormality. It is important that leads are placed in the same positions each time in order to achieve precise ECG recordings. If a machine-read QTc value is prolonged, as defined above, repeat measurements may not be necessary if a qualified physician's interpretation determines that the QTc values are in the acceptable range.

### 8.2.4 Clinical Laboratory Tests

All details regarding clinical laboratory sample collection, preparation, and shipment are included in the laboratory manual provided by the CRO. In the event of abnormal clinical laboratory values,

the physician will make a judgment as to whether or not the abnormality is clinically significant and/or is deemed an AE.

#### 8.2.4.1 Laboratory Parameters

Clinical safety laboratory tests will be conducted as outlined in the Schedule of Assessments, and should be completed pre-dose. Laboratory tests will include the following:

##### **Serum Chemistry**

Albumin  
Alkaline phosphatase  
Alanine aminotransferase (ALT; SGPT)  
Amylase  
Aspartate aminotransferase (AST; SGOT)  
Bicarbonate  
Blood urea nitrogen  
Calcium  
Chloride  
Creatinine  
Creatine kinase and MB subtype (if elevated)  
(% and total MB)  
Gamma-glutamyl transferase  
Glucose  
Lactate dehydrogenase  
Lipase  
Magnesium  
Phosphate  
Potassium  
Sodium  
Total bilirubin  
Total cholesterol  
Total protein  
Triglycerides

##### **Hematology**

Hematocrit  
Hemoglobin  
Mean corpuscular hemoglobin  
Mean corpuscular volume  
Platelet count  
Red blood cell count  
White blood cell count with differential (%  
and absolute counts)

##### **Coagulation**

Prothrombin time  
Activated partial thromboplastin time  
International Normalized Ratio

##### **Additional Tests**

Serum hCG (women with childbearing  
potential only)  
Serum FSH (women only)  
HIV test  
HBsAg  
Anti-HCV  
VZV IgG

#### 8.2.4.2 Additional Tests

- Serum hCG will be performed at every visit for women with childbearing only.
- Serum FSH test can be performed to confirm postmenopausal status at screening only.
- Human immunodeficiency virus (HIV), hepatitis B (HBsAg), hepatitis C virus (RIBA 2 or 3), and VZV IgG antibody will be performed at screening only.

### 8.2.4.3 Sample Collection, Storage, and Shipping

Blood samples for hematology, coagulation parameters, serum chemistry, HIV and hepatitis screens, serum hCG (women with childbearing potential only), and serum CRP will be collected according to the laboratory manual provided by the CRO and according to the Schedule of Assessments and descriptions of visits.

### 8.2.4.4 Blood Volume

The total blood volume to be collected for clinical laboratory tests during the study is less than 150 mL.

## 8.3 Efficacy Assessments

- Total Mayo Score (Stool frequency, rectal bleeding, endoscopic findings [flexible proctosigmoidoscopy/colonoscopy], physician's global assessment): Screening and W8
- Partial Mayo Score: Baseline, W4, W8, W12, and W16
- Histologic Assessment of Endoscopic Biopsy: Screening and W8
- UCEIS score: Screening and W8
- SIBDQ: Baseline, W4, W8, W12, and W16
- Serum CRP: Baseline, W4, W8, W12, and W16
- Fecal calprotectin: Baseline, W4, W8, W12, and W16
- Fecal lactoferrin: Baseline, W4, W8, W12, and W16

### 8.3.1 Mayo Score

The Total Mayo score is an instrument designed to measure disease activity of ulcerative colitis, with scores ranging from 0 to 12 points. The Total Mayo score consists of 4 subscores, each graded from 0 to 3 with higher scores indicating more severe disease (Mayo scoring system is listed in Appendix 1). For the endoscopic subscore, the Modified Mayo Endoscopic Score will be used to exclude any friability from Grade 1 per the FDA guidance.

- Stool frequency (0-3)
- Rectal bleeding (0-3)
- Findings of endoscopy (0-3)
- Physician global assessment (PGA) (0-3)

The Partial Mayo score consists of 3 subscores (stool frequency, rectal bleeding, and PGA). The subscores of stool frequency and rectal bleeding will be answered by a patient and the subscore of PGA will be assessed by an investigator.

### 8.3.2 Endoscopy with Biopsy Procedure

All details regarding endoscopic examination, standardized performing procedures, video recordings, assessment, biopsy sampling procedures, storage, and shipping will be provided in the laboratory manual by the CRO.

Endoscopy examination (flexible proctosigmoidoscopy/colonoscopy) will be required at screening in order to establish the Mayo endoscopic subscore and confirm patient eligibility for the study at baseline. Mayo endoscopic subscores will be assessed by both local and central reader. If the single central reader and local reader assessment results do not match, another central reader will score for adjudication.

Any patient who has not had a colonoscopy performed within 10 years since the onset of symptoms will be required to undergo a colonoscopy for screening surveillance. Therefore, in such cases, a colonoscopy will be required at screening (a flexible proctosigmoidoscopy will not be an option).

An appropriately trained endoscopist should perform the flexible proctosigmoidoscopy/colonoscopy. Where possible the same endoscopist should perform the endoscopy for both screening and Week 8 visits. If this is not possible, it should be clearly documented who performed each endoscopy procedure.

### 8.3.3 Ulcerative Colitis Endoscopic Index of Severity (UCEIS)

The Ulcerative Colitis Endoscopic Index of Severity (UCEIS) is the first validated index for the assessment of overall endoscopic activity ([Appendix 2](#)). The final model incorporates the vascular pattern, the presence of bleeding and the presence of ulcerations with accurate definitions and 3 or 4 levels of severity as measurable parameters, which explain almost 90% of variations in determining overall activity.

### 8.3.4 Quality of Life Questionnaire: Short Inflammatory Bowel Disease Questionnaire (SIBDQ)

The SIBDQ is a health-related quality of life (HRQoL) tool measuring physical, social, and emotional status. Scores range between 10 and 70, reflecting poor to good HRQoL. The SIBDQ has been predominantly used in trials for Crohn's disease, and further validation of the SIBDQ is desirable in UC patients. A sample of the SIBDQ is provided in [Appendix 3](#).

### 8.3.5 Biomarkers

The following biomarkers will be analyzed to support the efficacy assessments:

- Serum C-reactive protein (CRP)
- Fecal calprotectin
- Fecal lactoferrin

Instructions for storage and shipment of biomarker samples will be provided by the CRO.

## **8.4 Pharmacokinetic Assessments**

### **8.4.1 Plasma Pharmacokinetics**

For all patients, blood samples (approximately 4 mL) for analysis of BBT-401-1S pharmacokinetics will be collected in blood collection tubes containing K2EDTA as anticoagulant at the following scheduled time points:

- Visit 2 (Baseline) and Visit 3 (W4): pre-dose and 3 hour ( $\pm$  15 minutes) and 6 hour (- 30 to + 150 minutes) post-dose.
- Visit 4 (W8): pre-dose only

Blood tubes will be gently inverted several times to ensure mixing and placed on wet ice. Plasma will be obtained within 2 hours of blood collection by centrifugation approximately at 3200 g and at 4 °C for 10 minutes. Plasma will be transferred into two labeled plasma collection tubes each containing approximately 0.8 mL and stored in freezing conditions (-20 °C or below) until shipment to an analytical lab. Blood sampling, centrifuge time, storage condition, and storage time will be documented.

Instructions for sample shipment will be provided in a separate document by the Sponsor. Plasma sample analysis will be performed using a validated bioanalytical method.

### **8.4.2 Tissue Concentration**

For all patients, biopsy samples for analysis of BBT-401-1S concentration will be collected in tissue collection tubes during the endoscopy following Visit 1 (Screening) and prior to Visit 4 (W8).

The collection tubes will be stored in freezing conditions (-20 °C or below) until shipment to an analytical lab. Tissue sampling, storage condition, and storage time will be documented.

Instructions for sample shipment will be provided in a separate document by the Sponsor. Tissue sample analysis will be performed using a non-validated bioanalytical method.

## **8.5 Adverse Events and Serious Adverse Events Reporting**

### 8.5.1 Definition of Adverse Events (AE)

An adverse event (AE) is any untoward medical occurrence in a patient administered a pharmaceutical product, which does not necessarily have a causal relationship with the treatment. An AE can be any unfavorable and unintended sign (e.g., including an abnormal laboratory finding), symptom, or disease temporally associated with the use of the study drug, whether or not it is considered to be study drug related. This includes any newly occurring event or previous condition that has increased in severity or frequency since the administration of study drug.

Note that progression of the ulcerative colitis investigated in this protocol, including secondary events that are subsumed under a unifying diagnosis of disease progression, will NOT be considered an AE unless the investigator judges the progression to be related to treatment with study drug.

An AE includes, but is not limited to, the following:

- Any clinically significant worsening of a pre-existing condition
- An AE occurring from overdose (i.e., a dose higher than that indicated in the protocol) of a study drug, whether accidental or intentional
- An AE occurring from abuse (e.g., use for nonclinical reasons) of a study drug
- An AE that has been associated with the discontinuation of the use of a study drug
- Any treatment-emergent abnormal laboratory result that is clinically significant, i.e., meeting 1 or more of the following conditions, should be recorded as a single diagnosis on the AE page in the eCRF:
  - Accompanied by clinical symptoms
  - Leading to a change in study medication (e.g., dose modification, interruption or permanent discontinuation)
  - Requiring a change in concomitant therapy (e.g., addition of, interruption of, discontinuation of, or any other change in a concomitant medication, therapy or treatment)

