### 6.3 Measures to Minimize Bias: Randomization and Blinding

A total of 16 subjects in each of the 3 dosing cohorts will be randomized to either active or placebo group in a 3:1 ratio (12 active and 4 placebo) using the electronic data capture (EDC) system.

The randomization code will be generated by a unblinded statistician who is not involved with the study. The Sponsor, investigators, patients, and CRO and other relevant personnel involved with the conduct of the study, with the exception of clinical supply staff and the unblinded statistician, will be blinded to the identity of study medication.

For the 1st or 2nd cohort, if the 12th patient (75%) completes Visit 4 (Week 8), the CRO data management (DM) team confirm all clinical data of the 12 patients have no issue and then obtain the written consent from the Sponsor to breaking the code. Per the request of the CRO DM team, the randomization codes of the 12 patients will be opened via the unblinded statistician and notified to the Sponsor for the analysis to determine the next dose. After confirming all clinical data of remaining 4 patients for the 1st or 2nd cohort, the randomization codes will be subsequently opened to the sponsor through the same procedures stated above.

After the last patient of last cohort completes the SFU, the CRO DM team confirm the whole clinical database has no issue and then request the database lock to the Sponsor. Per the Sponsor's approval on the database lock, the randomization code of all patients will be opened via the unblinded statistician and notified to the CRO for the statistical analysis.

Breaking of the randomization code without Company's permission is expressly forbidden except in the event of a medical emergency where the identity of the study medication must be known in order to properly treat the patient. In the event of a medical emergency, it is requested that the investigator make every effort to contact the study monitor or designee prior to breaking the code.

If the blind is broken due to the medical emergency, the subject must be early terminated; a written explanation must be prepared immediately.

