### 8.5.2 Definition of Serious Adverse Events (SAE)

A serious adverse event (SAE) is any AE, occurring at any dose and regardless of causality that:

- Results in death
- Is life-threatening “Life-threatening” means that the patient was at immediate risk of death from the reaction as it occurred, i.e., it does not include a reaction that hypothetically might have caused death had it occurred in a more severe form.
- Requires inpatient hospitalization or prolongation of existing hospitalization (see clarification in the paragraph below on planned hospitalizations)

- Results in persistent or significant disability/incapacity “Disability” is defined as a substantial disruption of a person’s ability to conduct normal life functions.
- Is a congenital anomaly/birth defect
- Is an important medical event

An “important medical event” is an event that may not result in death, be life-threatening, or require hospitalization but may be considered an SAE when, based upon appropriate medical judgment, it may jeopardize the patient and may require medical or surgical intervention to prevent 1 of the outcomes listed in the definitions for SAEs. Examples of such medical events include allergic bronchospasm requiring intensive treatment in an emergency room or at home, blood dyscrasias or convulsions that do not result in inpatient hospitalization, or the development of drug dependency or drug abuse.

Clarification should be made between the terms “serious” and “severe” because they are not synonymous. The term “severe” is often used to describe the intensity (severity) of a specific event (as in mild, moderate, or severe myocardial infarction); however, the event itself may be of relatively minor medical significance (such as a severe headache). This is NOT the same as a “serious” adverse event (SAE), which is based on patient/event outcome or action criteria described above. An SAE is usually an event that poses a threat to a patient’s life or ability to function. In contrast, an AE assessed as “severe” is not automatically considered “serious” in nature (i.e., an SAE). For example, persistent nausea of several hours duration may be considered severe nausea but not an SAE. On the other hand, a stroke resulting in only a minor degree of disability may be considered mild, but would be defined as an SAE based on the above noted criteria. Seriousness (not severity) serves as a guide for defining regulatory reporting obligations.

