## **10.7 Safety Oversight**

The study will be monitored by the Safety Monitoring Committee (SMC) comprised of the Principal Investigator for each site, the Medical Monitor, and Sponsor representative(s) or designee. During the study period, all SAEs or safety issues will be sent to the SMC on a continual basis. The SMC will be responsible for reviewing all SAEs or safety issues and making the decision of proceeding to a new dose level after completing each cohort based on the relevant safety data. If at any point a safety concern arises, an ad hoc meeting of the SMC can be performed.

Further information describing a scope of work and procedures for the SMC will be provided in the SMC Charter.

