4.5 Handling of Dropouts or Missing Data

No adjustments for missing data and no imputation methods are planned for this study.

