4.8.1 Adverse Events

An AE is defined as any untoward medical occurrence in a subject who is administered a medicinal product and that does not necessarily have a causal relationship to the treatment. All AEs will be included in the data listings. Verbatim terms on case report forms will be mapped to preferred terms and system organ classes (SOC) using the Medical Dictionary for Regulatory Activities (MedDRA) (version 19.1).

A Treatment Emergent Adverse Event (TEAE) is defined as an adverse event that occurs or worsens on or after the first dose of study drug. TEAE summary will be displayed by cohort and treatment. Unless otherwise specified, summaries that are displayed by SOC and preferred terms will be ordered alphabetically by SOC, and within each SOC, preferred terms will also be ordered alphabetically. Summaries of the following types will be presented:

- Subject incidence of TEAEs by MedDRA SOC and preferred term.
- Subject incidence of TEAEs by MedDRA SOC, preferred term, and severity. Severity will be recorded as deemed by investigator. At each level of subject summarization, a subject is classified according to the highest severity if the subject reported one or more events.
- Subject incidence of study drug related TEAEs by MedDRA SOC and preferred term.
- Subject incidence of TEAEs by descending incidence of preferred terms.
- Subject incidence of serious TEAEs by MedDRA SOC and preferred term, if applicable.
- Subject incidence of TEAE leading to early termination by MedDRA SOC and preferred term, if applicable.

For each subject and for each adverse event, the duration of the event will be calculated as:

$$\text{Duration of AE} = \text{AE stop date} - \text{AE start date} + 1$$

The duration of AEs will be displayed in the data listing.

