	16.2.6.3	Histologic Assessment of Endoscopic Biopsy
	16.2.6.4	Ulcerative Colitis Endoscopic Index of Severity
	16.2.6.5	Short Inflammatory Bowel Disease Questionnaire
	16.2.6.6	Biomarkers
16.2.7		Adverse Events Listings
	16.2.7.1	Adverse Events
	16.2.7.2	Serious Adverse Events
	16.2.7.3	Adverse Events Leading to Permanent Withdrawal of Study Treatment or Discontinuation from the Study
	16.2.7.4	Adverse Events Leading to Death
16.2.8		Individual Lab Measures
	16.2.8.1	Hematology
	16.2.8.2	Chemistry
	16.2.8.3	Vital Signs
	16.2.8.4	Electrocardiogram
	16.2.8.5	Physical Examination
16.2.9		Pharmacokinetics
	16.2.9.1	Individual Plasma Concentration Data
	16.2.9.2	Individual Tissue Concentration Data
16.2.10		Other Miscellaneous Data
	16.2.10.1	Randomization
	16.2.10.2	IP
	16.2.10.3	Investigator Signature

Table 14.1.1
Summary of Patient Disposition
All Patients

	Placebo n %	BBT-401-1S n %	All Subjects n %
Screened	xx	xx	xx
Randomized			
Site Number 01	xx	xx	xx
Site Number 02	xx (XX.X)	xx (XX.X)	xx (XX.X)
...	xx (XX.X)	xx (XX.X)	xx (XX.X)
Modified Intent-to-Treat (mITT)	xx (XX.X)	xx (XX.X)	xx (XX.X)
Per-Protocol	xx (XX.X)	xx (XX.X)	xx (XX.X)
Safety	xx (XX.X)	xx (XX.X)	xx (XX.X)
Pharmacokinetics (PK)	xx (XX.X)	xx (XX.X)	xx (XX.X)
Dosed [1]	xx (XX.X)	xx (XX.X)	xx (XX.X)
Completed Initial 8-Week Treatment			
Yes	xx (XX.X)	xx (XX.X)	xx (XX.X)
No	xx (XX.X)	xx (XX.X)	xx (XX.X)
If No, Reason for Early Termination of Initial 8-Week Treatment			
Subject's request or request of legal representative	xx (XX.X)	xx (XX.X)	xx (XX.X)
Per Principal Investigator, continuation would be detrimental to subject's well-being	xx (XX.X)	xx (XX.X)	xx (XX.X)
Sponsor request	xx (XX.X)	xx (XX.X)	xx (XX.X)
Withdrawal of consent	xx (XX.X)	xx (XX.X)	xx (XX.X)
Significant Protocol Deviation	xx (XX.X)	xx (XX.X)	xx (XX.X)
Non-compliance with the protocol or study drug	xx (XX.X)	xx (XX.X)	xx (XX.X)
Clinical Progression	xx (XX.X)	xx (XX.X)	xx (XX.X)
Adverse Event	xx (XX.X)	xx (XX.X)	xx (XX.X)
Lost to follow-up	xx (XX.X)	xx (XX.X)	xx (XX.X)
Death	xx (XX.X)	xx (XX.X)	xx (XX.X)
Other	xx (XX.X)	xx (XX.X)	xx (XX.X)
Completed Visit 6 (Week 16)			
Yes	xx (XX.X)	xx (XX.X)	xx (XX.X)
No	xx (XX.X)	xx (XX.X)	xx (XX.X)

[1] 'Dosed' is defined as all randomized patients who received at least one dose of study medication.

Note: Percentages are based on the number of subjects randomized.

Bridge Biotherapeutics, Inc.
 PROTOCOL: BBT401-UC-US02
 Draft Version (to mention only if not final)

Confidential

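### UC worsening judged unrelated to study drug is exempt from AE and SAE reporting even if it leads to hospitalisation or withdrawal, and if the patient leaves before Week 8 the outcome is also missing from the endoscopy-based efficacy results

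*Protocol*

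**What the plan says.** **AE definition.** Protocol 8.5.1 sets aside progression of the UC under study, together with events covered by that diagnosis: it "will NOT be considered an AE unless the investigator judges the progression to be related to treatment with study drug". The list of AEs in the same section includes "Any clinically significant worsening of a pre-existing condition", with no causality condition. Protocol 8.2.1 asks sites to record clinically important changes on physical examination as AEs and makes no exception for UC. SAP 4.8.1 states "An AE is defined as any untoward medical occurrence in a subject who is administered a medicinal product" and repeats no exemption.

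**SAE definition.** Protocol 8.5.2 begins "A serious adverse event (SAE) is any AE, occurring at any dose and regardless of causality that" and then lists the seriousness criteria, inpatient hospitalisation among them.

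**Who judges.** Protocol 6.3 names those who are blinded: "The Sponsor, investigators, patients, and CRO and other relevant personnel involved with the conduct of the study". The investigator therefore decides relatedness without knowing the arm.

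**Oversight.** Protocol 10.7 says "all SAEs or safety issues will be sent to the SMC on a continual basis". It also gives the SMC the decision to move to a new dose level, based on the relevant safety data.

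**Missing outcomes.** SAP 4.5 says "No adjustments for missing data and no imputation methods are planned for this study". SAP 4.12 and Protocol 9.4.1 agree. The shell for Table 14.1.1 includes "Clinical Progression" among the reasons for not completing the first 8 weeks.

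**The concern.** Exempting disease progression from AE reporting is defensible when the efficacy endpoints capture it. Here the endoscopy-based endpoints do so only for patients who have a Week 8 value, and no endpoint counts worsening or treatment failure.

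This is the first trial of the drug in patients with active UC, it escalates dose, and Protocol 6.1.2 acknowledges that an adequate safety database in such patients does not yet exist. Worsening colitis is therefore a safety outcome as well as an efficacy one. Whether it is recorded depends on a relatedness judgement that is hard to make, because the underlying disease is always available as another explanation. Protocol 8.5.3.2 allows a grade of not related when another cause is the most plausible.

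At stake are the SAE counts by arm and the information on which the SMC decides whether to escalate.

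**Working it through.** The plan gives no flare rate, dropout rate, standard deviation or sample size calculation, so it has no figure of its own to reproduce. The only inputs are the allocation (12 active + 4 placebo = 16 per cohort; 3 × 16 = 48) and the definitions.

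**1. Safety path of a flare judged unrelated.**
- Under the 8.5.1 exemption it is not an AE.
- Under 8.5.2 an event that is not an AE cannot be an SAE, even with hospitalisation. The phrase about causality in 8.5.2 does not help, because the causality test has already been applied at the AE step.
- It therefore enters none of Tables 14.3.1.1 to 14.3.1.6.
- There is no fallback. The further items that 8.5.2 wants handled like SAEs are pregnancy exposure, overdose, abuse, accidental exposure and device malfunction. Section 8.5.6 (events of special interest) is marked as not applicable.
- The broader definition in SAP 4.8.1 cannot restore the event, because the SAP tabulates what sites record.

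**2. The conflict.** The same flare is an AE under the pre-existing-condition item of 8.5.1, under 8.2.1 if it shows on physical examination, and under SAP 4.8.1. It is not an AE under the exemption. Two sites could record identical flares differently and each cite the protocol.

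**3. Efficacy path if the patient also leaves before Week 8.**
- Protocol 8.3 schedules Total Mayo, UCEIS and histology at Screening and Week 8 only. The shells show Baseline, Week 8 and the change.
- With one scheduled post-baseline visit, the repeated-measures model in SAP 4.7.1 has no earlier value to draw on, so a patient without Week 8 contributes nothing to the result.
- The per-protocol set (SAP 4.3.2) requires completion to Visit 4, so it drops the same patient.
- An early-termination (ET) visit is to be attempted, with Mayo score, endoscopy and UCEIS (Protocol 7.4). No rule assigns those values to Week 8, and the endoscopy form in Appendix 1 offers only Screening and Visit 4.
- Leavers are not replaced (Protocol 6.6.2).

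**4. If the patient is hospitalised but stays.** Visit 4 scores exist and the patient is in the efficacy tables. Only the gap in step 1 applies.

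**5. Size, on assumed inputs.**
- Share of an arm with an unreported event = k/n. Active: 1/12 = 8.3%, 2/12 = 16.7%, 3/12 = 25%. Placebo within a cohort: 1/4 = 25%.
- Chance of at least one such leaver in a cohort of 16, if each patient has probability d: 1 − (1 − d)^16. For d = 5%, 10%, 20% this is 0.56, 0.81, 0.97.
- Shift in an arm's mean Week 8 change when k such patients are missing, if their unobserved change is g Mayo points worse than that of the patients who remain: g × k/n.

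| Missing | g = 2 | g = 4 | g = 6 |
|---|---|---|---|
| 1 of 12 active | 0.17 | 0.33 | 0.50 |
| 2 of 12 active | 0.33 | 0.67 | 1.00 |
| 3 of 12 active | 0.50 | 1.00 | 1.50 |
| 1 of 4 placebo | 0.50 | 1.00 | 1.50 |

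The arm that loses the patient looks better than it should, so the comparison can be biased in either direction.

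**The case against.** The best defence is that such a patient does not vanish, and that is right. A dosed leaver stays in the Safety set and in the laboratory, vital sign and ECG tables. If in the mITT, the leaver is counted on the n (missing) line of the efficacy tables. ET values can appear in listings, and the disposition table may show the reason as clinical progression. Protocol 9.4.1 promises that all available data will be listed and tabulated. Protocol 9.5.2 asks for secondary endpoints at each timepoint, so a Week 4 Partial Mayo score may be shown even though the shells, made for the first cohort, show only Week 8. None of these places shows that a flare was serious, and the progression row competes with others such as withdrawal of consent.

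A reader might infer that the SMC would not see serious flares. The documents do not support that. The SMC receives safety issues as well as SAEs, its members include each site's principal investigator and the medical monitor, and the sponsor reviews all pertinent data before choosing the next dose (Protocol 6.1.2). What stands is narrower: the text does not require such a flare to be sent.

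A further point is that few flares may be graded unrelated, because the possibly related grade in 8.5.3.2 admits events that other factors could readily have caused. That could reduce the number of exempt events. It also shows that the outcome depends on individual judgement, and 8.5.1 does not say which of the four grades lifts the exemption.

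**Conclusion.** The concern holds on the text. A UC flare that leads to hospitalisation or withdrawal and is judged unrelated can be left out of every AE and SAE table under 8.5.1, while other passages would count it. If the patient also leaves before Week 8, the outcome is missing from the Total Mayo, UCEIS and histology results in both analysis sets.

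Two stronger readings are tempting and should not be adopted. One is that hospitalisation itself removes a patient from the efficacy tables; only a missing Week 8 value does that. The other is that such patients appear nowhere except in the disposition table; the objection lists where else they remain.

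The percentages and shifts in the working are illustrations on assumed event counts, rates and score gaps, none of which the documents supply. They show that in arms of 12 and 4 a single unrecorded event matters. They do not forecast how many will occur. This is a change worth making before further dose decisions; the design can stand without other alteration.

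**What to change.** Reconcile Protocol 8.5.1, 8.2.1 and SAP 4.8.1 by limiting the exemption to non-serious UC fluctuation. Record UC worsening as an AE, or as an SAE where it qualifies, whatever its relatedness, when it meets a seriousness criterion or leads to withdrawal from study drug or from the study. Add a line for these events by arm to the SAP and shells, and state in Protocol 10.7 that serious cases go to the SMC. The change concerns recording only and alters no treatment or stopping decision.

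The cost is an amended protocol passage with IRB review, one added SAP and shell line, possibly an SMC charter edit, and a few more AE and SAE reports.

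This closes the safety gap. It does not settle how ET values enter the Week 8 analysis; SAP 4.5 would have to state that separately.
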